## 1 LIST OF ABBREVIATIONS

AE	Adverse Event
ANCOVA	Analysis of Covariance
BMI	Body Mass Index
CRF	Case Report Form
CTC	Clinical Trial Centre
CVD	Cardiovascular Disease
eCRF	Electronic Case Report Form
DMP	Data Management Plan
EDC	Electronic Data Capture
EU	European Union
GCP	Good Clinical Practice
HDL-C	High-Density Lipoprotein Cholesterol
HKU	The University of Hong Kong
ICH	The International Council on Harmonisation of Technical Requirements for Registration of Pharmaceuticals for Human Use
IRB	Institutional Review Board
ITT	Intention-to-Treat
LDL-C	Low-Density Lipoprotein Cholesterol
PI	Principal Investigator
PP	Per-Protocol
TAG	Triglycerides
TC	Total Cholesterol
UP	Unanticipated Problems
US FDA	United State Food and Drug Administration

### 3 PROTOCOL SYNOPSIS

**Title:** The Effect of Soya Beverage Fortified with Plant Sterol on Major Serum Lipids in Normocholesterolemic, Healthy Southern Chinese Individuals

**Phase:** Phase II

**Study Site:** Queen Mary Hospital, The University of Hong Kong

**Study Design:** This is a local, single-center, two-arm, randomized, double-blind, placebo-controlled study that examine the effect of the consumption of a soya beverage enriched with plant sterol for 3 weeks. Subject will be randomly assigned to receive either the investigational or control product. The randomization will be stratified by both gender (male and female) and age group (18-40 years and >40 years).

Blood specimens will be collected at the baseline and at the end of the consumption period, which will be subjected to laboratory analysis.

**Study Objectives:** **Primary Objective:** To examine the effect of the consumption of a plant sterols fortified soya beverage on serum LDL cholesterol in healthy, free-living normocholesterolemic individuals

**Secondary Objective:** To examine health-benefits by consuming the plant sterols fortified soya beverage in terms of serum total triglyceride, total and HDL cholesterol, other cardiometabolic risk factors and musculoskeletal-related traits.

**Study Population:** Two hundred (200) Southern Chinese male or female in Hong Kong who aged 18 or above with good general health will be recruited in this study.

**Investigational and Control Product Administration:** The investigational product is a soya drink fortified with 2g plant sterols per pack and the control product is the same soya drink except without plant sterols.

Subjects will be asked to consume 1 pack of either investigational or control product daily for 3 consecutive weeks, each pack consumed once with main meal. Subjects consuming test product will therefore consume 2 g of plant sterols daily.

**Study Duration:** This study is estimated to last for 12 months (from subject enrollment until completion of data analyses)

**Subject Participation Duration:** 3 weeks

**Estimated Time to Complete Enrollment:** 9 months

**Study Endpoints:** **The primary endpoint** is the mean serum LDL-C at the end of week 3 after the consumption of plant sterols fortified soya beverage or control product.

**The secondary endpoints** include the changes of serum LDL-C, HDL-C, total cholesterol, triglycerides (TAG), serum creatinine, fasting blood glucose, other cardiometabolic risk factors and musculoskeletal-related traits from baseline to week 3.

**Statistical Analysis:** **Sample size rationale:**

The sample size calculation is based on ANCOVA with baseline serum LDL-C as independent covariate. According to a previous study (36), the standard deviation of LDL-C at week 4 is approximately 0.85 mmol/l and the estimated correlation coefficient between the outcomes measured at baseline and week 4 is about 0.7. In addition, a minimum difference of 0.28 mmol/l in LDL-C between the groups is considered clinically important.

By using PASS 12 for the sample size calculation, a power of 0.8 and a 5% of the maximum tolerable false positive rate, 75 subjects per group is required to detect the minimum difference between the mean values of LDL-C.

Considering an attrition rate of 25%, a total of 200 subjects will be recruited.

**Data set analyzed:**

The intention-to-treat (ITT) population is consisted of all randomized subjects. The per-protocol (PP) population includes all eligible subjects who have 80% of study product compliance, efficacy data collected within the pre-specified allowable visit window, and no protocol violation that is clinically significant.

**Handling of missing or invalid data:**

No data imputation will be performed to replace missing or invalid data.

**Efficacy Analysis:****Primary Efficacy Analysis:**

ANCOVA will be carried out to compare the serum LDL-C level at week 3 between the groups. The baseline of the response outcome will be used as a covariate to control for initial group differences. A log transformation will be performed if the normality assumption for the ANCOVA model is violated. And if the normality assumption is still not sustained, non-parametric approach might be performed. The primary efficacy analysis will be performed on both the ITT and the PP populations.

**Secondary Efficacy Analyses:**

Stratified analysis for the primary endpoint will be performed using the ANCOVA model adjusted for gender and age group. Subjects will be classified to one of the following strata:

1. Male, aged 18-40 years
2. Male, aged >40 years
3. Female, aged 18-40 years
4. Female, aged >40 years

The changes of the following response outcomes from baseline to week 3 will be summarized by descriptive statistics:

- Blood Tests: LDL-C, HDL-C, total cholesterol, TAG, creatinine and fasting glucose.
- Cardiometabolic risk factors: blood pressure, body temperature, weight, BMI, waist and hip circumferences.
- Musculoskeletal-related traits: handgrip strength, peak expiratory flow rate, bio-impedance, gait speed and body balance

[figure not shown]
The secondary efficacy analyses will be performed on the ITT population only.

***Safety Analysis:***

The incidence of AE such as nausea, abdominal cramps, vomiting, diarrhea, and flatulence will be summarized by frequency tables per study group. Data listings will be reported.

#### 4 SCHEMATIC OF STUDY DESIGN

#### Remarks

Subjects will be asked to refrain from drinking 2 alcoholic or caffeinated beverages per day and advised to maintain their typical diet and physical activity levels. They will also be asked to report any changes in diet or physical activity and symptoms or changes in health and medications throughout the trial.

## 5 SCHEDULE OF STUDY ASSESSMENTS / PROCEDURES

Assessments / Procedures	Screening & Baseline (Day 0)	End of Study (Day 21 ± 5)	Early Withdrawal
Informed Consent Form Signed	X		
Eligibility Criteria	X		
Demographic Information	X		
Medical History	X		
Physical Examination	X	X	X
Cardiometabolic Risk Factors 	X	X	X
Blood Test 	X	X	X
Concomitant Medications	X	X	X
Dispensing Study Product	X		
Adverse Events		X	X
Study Product Compliance		X	X
Dietary Information	X	X	X

### Remarks:

- Cardiometabolic risk factors include blood pressure, body temperature, body height and weight, waist and hip circumferences. Body height will be measured at the baseline only.
- Blood tests include:
  - Lipid profile: Serum level of LDL-C, HDL-C, total cholesterol and TAG
  - Serum creatinine, fasting blood glucose
- Physical examination includes measurement of bioimpedance. Participants with metal implant will be excluded from this measurement.

## 6 INTRODUCTION

### 6.1 Background Information

#### 6.1.1 *Disease Background Relevant to Clinical Study*

##### The Relationship Between Cardiovascular Disease (CVD) and Low-Density Lipoprotein Cholesterol (LDL-C)

A cardiovascular disease (CVD) is a major health problem as the third leading causes of mortality in Hong Kong (3). A number of CVD risk factors have been identified, such as hypertension, obesity, tobacco exposure and physical inactivity. Among these risk factors, elevated plasma LDL-C levels play a significant role in CVD development. The deposition of cholesterol in the arterial wall by the infiltration of LDLs is a key step in the development of atherosclerotic CVD such as coronary artery disease, stroke and peripheral vascular disease. The consensus of LDL as the major proatherogenic lipoproteins in the circulation provides a valuable parameter for assessing CVD risk (4). Indeed, blood LDL-C level is also one of the predictors in the Framingham Risk Score, a risk assessment tool widely used in clinical setting for estimating of 10-year cardiovascular risk of an individual (5).

The blood cholesterol level is controlled by cholesterol absorption from the diet and by endogenous cholesterol synthesis that occurs through a series of pathways. The main strategy of conventional lipid lowering therapy is to interfere with some of these pathways by pharmacological agents and dietary components (6). For example, statins are a class of highly effective cholesterol-lowering drugs by inhibiting the enzyme HMG-CoA reductase, which plays a central role in the production of cholesterol in the liver (7). Despite the various lipid lowering agents for the management of hyperlipidemia, a significant number of patients do not reach their LDL-C target goals due to various reasons such as low drug compliance and resistant to lifestyle change (7-8). The often poor achievement of LDL-C goals among high risk patients warrants the need of other cholesterol lowering measures with higher efficacy and patient acceptance.

### **6.1.2 Investigational Product Background Relevant to Clinical Study**

#### Plant Sterols and their Physiological Characteristics

Plant sterols are the naturally occurring functional equivalent of mammalian cholesterol. The most common plant sterols include sitosterol, campesterol, and stigmasterol. Plant sterols differ structurally from cholesterol by a methyl or ethyl group in their side chains and are not synthesized by the human body. These structural differences render them minimally absorbable in the intestine, of the fraction of 0.5-2% for plant sterols (9). As a result of low absorption and efficient excretion after uptake by the liver, circulating levels are low, varying from 0.3-1.0 mg/dL for plant sterols. Phytosterol-enriched foods and dietary supplements have been marketed for decades. The main food sources of plant sterols are vegetable oils, margarines, breads, cereals, and vegetables, contributed 50-80% of the daily plant sterol intake (11-12).

#### Lipid-Modifying Effect of Plant Sterols

The cholesterol lowering effect of plant sterols were demonstrated more than 50 years ago (13). Earlier studies demonstrated that pure plant sterol supplementation lowered both total serum cholesterol and LDL-C in individuals with hypercholesterolemia (14). A number of clinical trials have been examined the efficacy of plant sterols/stanols as a cholesterol lowering agent when incorporated into low fat foods including yoghurt, bread and cereal (15). Results from several epidemiological studies consistently reported that dietary incorporation of plant sterols/stanols (1.5-2 g/day) reduces serum LDL-C levels 5% to 15% with minimal adverse events (16-18). In addition, the impact of the consumption of plant sterols/stanols-enriched foods is relatively consistent in both normolipidemic and dyslipidemic individuals including those treated with lipid-lowering agents, regardless of background diet and that there is little or no effect on high-density lipoprotein (HDL) cholesterol or triglyceride (TAG) levels (19-20). It has now been recognized by the United States Federal Drug Administration (US FDA) and the American Heart Association that dietary incorporation of plant sterols is recommended for blood cholesterol reduction and thereby reducing the risk of CVD (21-22).

## Potential Mechanisms of Action of Plant Sterols

*Several studies have investigated the mechanism of action of phytosterols on reducing serum LDL-C level (23-24). The initial stage of intestinal handling of phytosterols from diet is essentially similar to the absorption of cholesterol, involving emulsification, hydrolysis and micellar transport (25). However, most of plant sterols/stanols are pumped back into the gut lumen via the ATP-binding cassette co-transporters G5 and G8 (ABCG5/ABCG8), resulting in the minimal entry of these plant-derived molecules into the circulation. The hypocholesterolemic effects of plant sterols/stanols is explained by an inhibition of cholesterol absorption, which is ascribed to a competition with intestinal cholesterol for incorporation into mixed micelles (26), although other possible mechanistic explanation have been proposed (27).*

## Clinical Significance

The goal of this study is to determine the efficacy of regular consumption of plant sterols-enriched soya beverage in reducing serum LDL-C level among Southern Chinese individuals. The hypocholesterolemic effects of plant sterols with soya milk as carrier has only been investigated in few studies, the beneficial effects of soya beverage fortified with plant sterols on Southern Chinese individuals are not well-understood and necessitate investigation. Results from this study will have important clinical implications in the control and management of blood LDL-C level among normolipidemic individuals and will promote further development of novel soya beverage or related products containing plant sterols for future use in cholesterol-lowering initiatives. In addition to a role in primary prevention in the general population, functional food enriched with plant sterols may provide additional LDL-C lowering benefit in dyslipidaemic patients at high CV risk as an adjunct to traditional pharmacologic therapy.

## **6.2 Study Rationale**

Eligible Southern Chinese in Hong Kong aged 18 or above with good health condition will be asked to consume 2g of plant sterols orally per day for 3 consecutive weeks as provided by one pack of plant sterols-containing soya beverage, each pack consumed during the main meal every day. The dosage regime is designed in accordance with the recommendations from European Union (EU) Register of Nutrition and Health claims as well as previous clinical trials and epidemiological studies regarding the same study ingredient (13-18). It is hypothesized that daily consumption of 2g of plant sterols in a soya beverage results in a significant reduction of serum LDL-C.

*Result from this study encourages further development of novel soya beverage or related products containing plant sterols for future use in cholesterol-lowering initiatives*

*among Chinese population.*

## *Potential Risks and Benefits*

### **6.2.1 Potential Risks**

- This study does not involve any pharmacological intervention. Pre-clinical and previous clinical trials (13-18) indicated that the study product is generally safe and will not affect the health status of the subjects. Therefore, additional risk will be minimal.
- Blood samples will be taken at the start and the end of the study by a registered nurse. Venipuncture may result in pain or bruises. The chance of infection associated with venipuncture is very low.

### **6.2.2 Potential Benefits**

- Subjects will receive an assessment of their current health status and they will be informed if any test result shows a potential risk to their health condition.
- Previous studies have demonstrated that regular consumption of plant sterols may reduce total blood cholesterol and LDL-C level. Reduction of LDL-C levels has been demonstrated to significantly reduce CVD morbidity and mortality (13-18).
- While it is possible, however, that subjects may not obtain any direct benefits in this clinical study, the information obtained from this study maybe useful to scientific community to examine the efficacy of plant sterols for future use in cholesterol-lowering initiatives and prevention of cardiovascular disease.

## 7 OBJECTIVES

### 7.1 Study Objectives

- **The primary objective** of this study is to assess the efficacy of daily consumption of 2g plant sterols as provided by one pack of 250 ml soya beverage product each taken during the main meal for 3 consecutive weeks, in lowering the blood LDL-C level among Southern Chinese.
- **The secondary objective** is to examine if there is other health-benefits by consuming the plant sterols-enriched soya beverage, such as glucose and TAG lowering effect.

## 8 STUDY DESIGN

The study is a 3-week, single-center, double-arm, randomized, double-blind clinical study. Healthy, normocholesterolemic Southern Chinese in Hong Kong will be recruited and screened by the inclusion and exclusion criteria.

Two hundred (200) eligible and consented subjects will be assigned to consume either the investigational or control product by stratified randomization, according to the instructions as follows:

- Investigational Group: Daily consumption of 2g of plant sterols as provided by one pack of the plant sterols-enriched soya beverage for 3 consecutive weeks, each pack consumed during the main meal
- Control Group: Daily consumption of one pack of the soya beverage without plant sterols for 3 consecutive weeks, each pack consumed during the main meal

The randomization will be stratified by both gender (male and female) and age group (18-40 years and >40 years).

Subjects will be invited to attend a baseline visit (Day 0), after which study products will be administered for 21 days. A follow-up assessment (Day 21±5) at the end of the study intervention will be performed for outcome assessment. Clinical data and blood specimen will be obtained by trained personnel in both visits. All blood specimens will be analyzed in a centralized and certified clinical laboratory.

Subjects will be asked to refrain from drinking 2 alcoholic or caffeinated beverages per day and advised to maintain their typical diet and physical activity levels. They will also be asked to report any changes in diet or physical activity and symptoms or changes in health and medications throughout the trial.

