### **11.2 Dosage, Preparation and Administration of Study Products**

Investigational Group: Subjects will orally consume 2g of plant sterols daily as provided by one pack of the soya beverage for 3 consecutive weeks, each pack consumed during the main meal.

Control Group: Subjects will orally consume one pack of the soya beverage except without plant sterols for 3 consecutive weeks, each pack consumed during the main meal.

Subjects will be advised to consume the products immediately once the package is opened and store the products in cool place.

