### **11.3 Accountability Procedures for the Study Products**

Study products will be distributed to subjects during their screening and baseline visit (Day 0).

All unused products have to be returned to the study staff in the final visit (Day 21  $\pm$ 5) which will be used as a count of subject's compliance with the study products.

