### 13.6 Study Product Compliance

At the end of the study intervention period, subjects need to return all the excess soya beverage packs for counting the measure of compliance.

The study product compliance is calculated by the following equation:

- Study Product Compliance (%) =  $\frac{\text{Observed Consumption}}{\text{Expected Consumption}} \times 100\%$
- Observed consumption = Pack of soy milk dispensed – Pack of soy milk returned
- Expected consumption =  $\sum$  (Expected daily consumption × Number of treatment days)

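### Dosing is fixed at 21 days but the primary LDL-C draw may fall up to Day 26, and nothing tells late attenders to keep taking product until the draw

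*Combined protocol and SAP*

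**What the plan says.** **Dosing length.** Section 8 (Study Design): "Subjects will be invited to attend a baseline visit (Day 0), after which study products will be administered for 21 days". Section 11.2 gives the same duration for the investigational arm: "Subjects will orally consume 2g of plant sterols daily as provided by one pack of the soya beverage for 3 consecutive weeks". The synopsis and the primary objective in Section 7.1 also specify three consecutive weeks.

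**Timing of the draw.** The next sentence of Section 8 reads: "A follow-up assessment (Day 21±5) at the end of the study intervention will be performed for outcome assessment". The synopsis says: "Blood specimens will be collected at the baseline and at the end of the consumption period". The plan therefore states that the draw belongs at the end of dosing, while the window runs from Day 16 to Day 26.

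**Supply and return.** Section 11.3 has product handed out on Day 0 without saying how many packs, and "All unused products have to be returned to the study staff in the final visit". Section 13.6 says: "At the end of the study intervention period, subjects need to return all the excess soya beverage packs".

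**Compliance and analysis sets.** Section 13.6 divides packs consumed by expected packs, using "Number of treatment days", which is not defined. Under Section 14.2, PP requires 80% compliance, a primary measurement inside the visit window and no clinically significant violation; ITT is everyone randomized. The Visit 2 procedures in Section 12.1.2 record compliance but do not list the date of the last pack.

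**The concern.** A fixed course of 21 days and a visit window that extends five days beyond Day 21 do not fit together for late attenders. Someone booked for Day 25 who follows the dosing text has finished the product days before the blood is taken. Nothing in the documents says to continue, and nothing in the analysis-set definitions separates that draw from one taken on product.

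Section 6.1.2 attributes the LDL-C effect to inhibited absorption of cholesterol in the gut, so some loss of effect after stopping is plausible. A loss in the sterol arm only would shrink the estimated difference and reduce power. The window is the same in both blinded arms, so the problem cannot create a false positive.

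**Working it through.** **Step 1: the plan's own sample size.** Inputs from Section 14.1: SD 0.85 mmol/l, baseline-to-follow-up correlation 0.7, difference 0.28 mmol/l, 5% false-positive rate (taken as two-sided), power 0.8.

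- Residual SD = 0.85 × √(1 − 0.7²) = 0.607.
- Noncentral t, df = 2n − 3: power is 79.6% at n = 74 and 80.1% at n = 75. The stated 75 per group reproduces.
- Dropout: 150 / 0.75 = 200. This also reproduces.

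**Step 2: product-free days under the literal text.** These are the full days between the last of 21 daily packs and the day of the draw. The start day is not stated, so both are shown.

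| First pack | Last pack | Draw days affected | Product-free days |
|---|---|---|---|
| Day 0 | Day 20 | 22 to 26 | 1 to 5 |
| Day 1 | Day 21 | 23 to 26 | 1 to 4 |

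**Step 3: does PP remove these draws?** The 80% criterion is read as at least 80%.

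- All 21 packs taken: 21/21 = 100% with a fixed denominator. If the denominator runs to the day before a Day-26 draw, it is 21/25 = 84.0% (Day 1 start) or 21/26 = 80.8% (Day 0 start). The subject stays in PP each time.
- Some packs missed, denominator to the day before the draw: at Day 26, 20/26 = 76.9% (Day 0 start) and 19/25 = 76.0% (Day 1 start) fail, while 20/25 = 80.0% passes. At Day 23, 19/23 = 82.6% and 19/22 = 86.4% pass.

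PP therefore drops some of the latest draws by accident of the denominator, and keeps the others.

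**Step 4: what dilution would cost.** Let L = (share of draws off product) × (mean share of the effect lost in those draws). Both factors are assumptions, because the documents give neither the distribution of visit days nor a rate of offset. The diluted difference is 0.28 × (1 − L).

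| Assumption | L | Difference (mmol/l) | Power, 75 per arm | Power, 100 per arm |
|---|---|---|---|---|
| None off product | 0 | 0.280 | 80.1% | 90.1% |
| 10% late, 10% of effect lost | 1% | 0.277 | 79.3% | 89.5% |
| 10% late, 25% of effect lost | 2.5% | 0.273 | 78.1% | 88.6% |

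Break-even values: with 75 per arm, power falls to 75% at L = 6.1% (difference 0.263). With no dropout, so 100 per arm, it falls to 80% at L = 13.7% (difference 0.242).

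**The case against.** The best reply is that the protocol does link dosing to the visit. The sentence after the 21-day statement puts the visit at the end of the intervention, and the synopsis puts the blood draw at the end of consumption. Because unused packs come back at the visit, a subject seen on Day 16 cannot complete 21 daily packs, so the visit already ends dosing for early attenders. A compliance formula with a number of treatment days, and the references to excess packs, also fit a course that varies by subject. On this reading, 21 days is nominal.

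Much of this stands. A reader might infer that the dosing text has no connection to the draw, or that late draws will in fact be off product; the documents support neither. They also mention administration instructions given at Day 0 (Section 12.1.1), label instructions (Section 11.1.2) and a manual of procedures (Section 13.8). None of these is available here, and any of them could contain a stop rule.

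What remains is that the link is described but not put into operation. The text we have does not tell a Day-25 attender what to do after three weeks, and its only explicit duration points to stopping. If continuation is intended, the fixed 21 days contradicts it for late visits.

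**Conclusion.** The point holds as a minor inconsistency. The intended link between dosing and the primary draw is stated, but for visits after Day 21 it conflicts with the fixed course and no rule resolves it. Taken literally, in-window draws can follow up to 4 or 5 product-free days, and PP does not reliably remove them.

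Any bias is toward no effect, and the false-positive rate is not inflated. The size is unknown. The mild cases cost about 1 to 2 points of power (80.1 − 79.3 = 0.8; 80.1 − 78.1 = 2.0), and both rest on assumed visit timing and assumed loss of effect.

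A reader might infer a serious loss of power. For example, visits spread evenly over Days 16 to 26, with the effect decaying after Day 21 with a half-life of 3 to 14 days, would give power of about 60% to 75.5% at 75 per arm (normal approximation). The documents support neither the even spread nor any half-life, so these figures should not raise the severity.

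**What to change.** 1. In Sections 8 and 11.2, state that one pack is taken daily for three weeks and continued until the day before the Visit 2 draw.
2. On Day 0, dispense enough packs to cover a Day-26 visit: 25 if dosing starts on Day 1, 26 if on Day 0. State which start day applies.
3. Record the dates of the first and last pack at Visit 2.
4. Define the number of treatment days in Section 13.6 as running from the first pack to the day before the draw.
5. Use the last-pack date for a sensitivity analysis of the primary endpoint that excludes draws taken more than a few days off product, with the cut-off fixed before unblinding.
6. Leave the ITT analysis unchanged. Do not make a pack on the day before the draw a condition of PP: that would remove highly compliant subjects who missed only the last one.

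**Cost.** Relative to 21 packs (the number now dispensed is not stated), this is 4 or 5 more per subject, or 800 to 1,000 for 200 subjects, plus two date fields and a few lines of text. The sample size does not change. The main downside is that days on product would vary with the visit date, from 15 to 25 (Day 1 start) or 16 to 26 (Day 0 start), around the three weeks in the primary objective. Early visits already produce the lower end of that range.
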